#### **9.5.2. Visit 2 (Day -7 ) Initiation of Baseline CGM Assessment and Diary Data Collection**

The subject will arrive at the clinic and the following procedures will be completed:

1. Eligibility review
2. Recording of the subject's insulin correction factor (i.e., the reduction in blood glucose in mg/dL per 1 unit of insulin taken).
3. Review Adverse Events
4. The subject will receive and be trained in the use of the glucose meter and strips for use in the study during the CGM data collections periods.
5. The study personnel will assist the subject with downloading the iPRO mylog App and creating the appropriate account to allow synchronization with the CGM data.
  - a. Each site is provided with their specific clinic i.d. from the sponsor
6. The subject will have the blinded iPRO2 CGM device assigned, inserted and initiated according to the manufacturer's instructions. The iPRO2 device ID will be logged for later entry into the eCRF.
7. The importance of using the study glucose meter no less than 12 hours apart will be emphasized for the subject.
  - a. Subjects must perform blood glucose readings at a minimum of twice per twenty-four hour period.
8. The subject's clinical practice glucose, insulin, diary and pump data, if applicable, leading up to the visit will be reviewed and any dose adjustments as required will be made.
  - a. An Insulin Diary will be provided to the subject to collect the following, daily:

- Total daily dose
  - Total Daily Bolus
  - Basal Rate
9. Schedule the subject's next visit and provide the following reminder:
- a. Subject should not administer any long acting insulin dose after dinner the day before the induction procedure.
  - b. Sensors will only hold 7 days of data. Should a subject receive an alert from the iPro app, S/He should contact the site for guidance.

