#### **9.5.4. Visit 4 – Safety check (Day 7±2)**

This visit can occur at any time of day as is least cumbersome for subject and clinic scheduling. The following will occur.

1. AEs since the last visit will be recorded.
2. Concomitant medication review.
3. Subject data including CGM, insulin utilization, electronic diary data will be uploaded to the MedTronic iPRO2 platform.
4. The subject's Omnipod will be removed.
5. The investigator or sub-investigator will use the modified Draize scales ([Appendix 4](#)) to assess erythema and edema formation at the injection site at 10±5 minutes following removal of the Omnipod. Any injection site with a score > 0 for either erythema or edema at 10 minutes post-dosing will be re-evaluated for both at 60±5 minutes post-dosing. If any scores remain > 1 at the 60-minute evaluation, the subject may leave the clinic but will be instructed to contact study staff if the condition fails to resolve.
6. Investigational Product and Omnipod accountability will be performed
7. The subject will load and initiate a new Omnipod with investigational product.
8. The subject will be given investigational product and Omnipods to cover time to next visit and will be instructed to exchange the Omnipod every 2-3 days.
9. Each time a new OmniPod is started local tolerability will be assessed as follows:
  - Subjects will complete a Visual Analog (VAS) questionnaire regarding infusion site discomfort ([Appendix 3](#)) at 10±5 minutes, at 30±5 minutes and again at 180±5 minutes following the injection of study drug.
  - Subjects will complete an Injection Site Discomfort Description and Duration Questionnaire ([Appendix 4](#)) at 10±5 minutes post-dosing. If discomfort is ongoing at 10 minutes post-dosing, the questionnaire will be completed again before the subject leaves the clinic to document the final duration.
10. The next visit will be scheduled
11. The subject will be reminded to keep his or her iPROmylog diary, bring used and unused Omnipods and investigational product vials back at the next visit

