#### **9.5.5. Visits 5 (Day 14±2)**

Visit procedures are identical to Visit 4 listed in section 9.5.4.

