#### **9.5.6. Visit 6 (Day 21±1)**

Visit procedures are identical to Visit 5 listed in section 9.5.4.

Additionally, the Insulin Diary will be given to the subject to collect the following, daily:

- Total Daily Dose
- Total Daily Bolus

- Basal Rate

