### 9.5.7. Visit 7 (Day 28±1)

The subject will fast after midnight the night before and arrive to the clinic at about 6-9 am the day of the planned hypoglycemia induction procedure. They will fast until the end of the hypoglycemia induction procedure the subsequent day. The subject will undergo the Hypoglycemia Induction Procedure as described in Section 9.4

1. AEs since the last visit will be recorded.
2. Concomitant medication review.
3. Assessment of vital signs, including measurement of BP, after a 5-minute seated rest
4. Physical examination, excluding breast, pelvic and genitourinary exams.
  - Measurement of height and weight
5. Performance of a 12-lead ECG (after subject has completed a 10-minute supine rest.)
6. Urine pregnancy test for women of childbearing potential.
7. Rapid urine drug screen.
8. The subject will have the following samples drawn:
  - CBC/CMP
  - Plasma glucagon (PK) before the Omnipod is removed
  - Immunogenicity sample
9. The subject's glucose, insulin, diary and pump data, if applicable, since the last visit will be reviewed. Subject data will be uploaded to the Medtronic Carelink Portal.
10. The Insulin Diary will be collected from the previous visit
11. The subject will complete the Gold Scale
12. The subject's Omnipod will be removed. Drug and Omnipod accountability will be completed.
13. The investigator will use the modified Draize scales (Appendix 5) to assess erythema and edema formation at the injection site at 10±5 minutes following removal of the Omnipod. Any injection site with a score > 0 for either erythema or edema at 10 minutes post-dosing will be re-evaluated for both at 60±5 minutes post-dosing. If any scores remain > 1 at the 60-minute evaluation, the subject may leave the clinic but will be instructed to contact study staff if the condition fails to resolve.
14. The subject will be reminded to refrain from using his or her own insulin until the hypoglycemia induction procedure is complete.
15. IV lines are inserted in both upper extremities for IV insulin and glucose infusion, and for venous sampling.
16. Plasma glucose is measured using a laboratory quality instrument, e.g. the YSI 2300 or 2900 that will be used for the clamping procedure.

17. Plasma Glucose will be maintained in the 80-120 mg/dL range until as described in section 9.4.
18. The subject will undergo the hypoglycemia induction procedure and normalization to euglycemia, per Section 9.4.

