**9.5.9. Visit 8 (Week 12±1 week)**

**CGM Resumption for 3-Month Follow Up**

This visit can occur at any time of day as is least cumbersome for subject and clinic scheduling. The following will occur.

1. Concomitant Medication Review
2. AEs since the last visit will be recorded.
3. The subject's dedicated blood glucose meter and iPRO2 recorder will be retrieved from storage and the subject will resume use as well as the iPRO2mylog diary with the insertion of a new CGM sensor.
4. The subject will be given a supply of BGM strips until the next visit a week later, to verify calibration of the CGM.
5. The Insulin Diary will be given to the subject to collect the following, daily:
  - Total Daily Dose
  - Total Daily Bolus
  - Basal Rate
6. The next visit will be scheduled.

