**9.5.10. Visit 9 (Week 13±1 Week) 3-Month Follow Up**

The subject will arrive to the clinic at about 6-9 am the day of the planned hypoglycemia induction procedure. The subjects will undergo this inpatient CRU visit.

1. AEs since the last visit will be recorded.
2. Concomitant medication review.
3. Assessment of vital signs, including measurement of BP, after a 5-minute seated rest
4. Urine pregnancy test for women of childbearing potential.
5. The subject will be reminded to refrain from using his or her own insulin until the hypoglycemia induction procedure is complete.
6. The subject will complete the Gold Scale

7. Subject data including CGM, insulin utilization, electronic diary data will be uploaded to the MedTronic iPRO2 platform.
8. The Insulin Diary will be collected from the previous visit.
9. IV lines are inserted in both upper extremities for IV insulin and glucose infusion, and for venous sampling.
10. Plasma glucose is measured using a laboratory quality instrument, e.g. the YSI 2300 or 2900 that will be used for the clamping procedure.
11. Plasma Glucose will be maintained in the 80-120 mg/dL range as described in section 9.4.
12. The subject will undergo the hypoglycemia induction procedure and normalization to euglycemia, per Section 9.4
13. The subject will have the following sample drawn:
  - Immunogenicity Sample

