**7.2.10.1 Weekly endpoints**

Additionally, all derived CGM endpoints will be derived on a weekly basis. The following weeks will be analyzed: Baseline (Week), Week 1, Week 2, Week 3, Week 4, Month 3 and Month 6. CGM-Derived parameters will be based on CGM data that fall in the following timeframe:

Week	Time window (Days)	
Baseline	7 days prior to day 1	
Week 1	1	7
Week 2	8	14
Week 3	15	21
Week 4	22	28
Month 3	7 days prior to date of Month 3 visit	
Month 6	7 days prior to date of Month 6 visit	

When deriving weekly endpoints - baseline will be based on the CGM data collected 7 days prior to the date/time of the first CSGI injection. For the AOC endpoint baseline will be the same as for the AOC calculated by day.

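### CGM visit windows allow sensor intervals longer than the stated 7-day capacity, and the SAP's Month 3 and Month 6 windows, counted back from the visit, can then discard recorded days

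*Protocol*

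**What the plan says.** **Sensor capacity.** Protocol 9.5.2, in the reminders given at Visit 2: "Sensors will only hold 7 days of data". Under 9.5 and Table 6, sensors are inserted and retrieved only at visits.

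**Treatment-phase visits.** The section headings give "Safety check (Day 7±2", "Visits 5 (Day 14±2", "Visit 6 (Day 21±1" and "Visit 7 (Day 28±1" (days). Table 6 differs: ±1 day for Visits 4 and 5, and Day 27-28±1 for Visit 7. No window refers to the previous insertion.

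**Follow-up visits.** A sensor goes in at "Visit 8 (Week 12±1 week" and comes out at "Visit 9 (Week 13±1 Week) 3-Month Follow Up". Visits 10 and 11 repeat this at Weeks 25 and 26, again with ±1 week each. The overview (Protocol 7.1) says retrieval is one week after insertion. The Visit 8 procedures (9.5.9) supply strips for one week until the next visit, and 9.5.11 applies the same procedures to Visit 10. Protocol 10 treats visits outside the windows as deviations and sets no limit on the interval between two visits.

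**Analysis windows.** SAP 7.2.10.1 assigns Weeks 1 to 4 by fixed study day. For follow-up it takes "7 days prior to date of Month 3 visit", with the same rule for Month 6. It does not mention insertion or recorded days. SAP 7.2.10 divides proportional time by the time recorded, but defines the rate of hypoglycemic episodes as a number of episodes with no time denominator. A minimum of 6 recorded days is required at baseline only (Protocol 9.5.3).

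**The concern.** Two separate mechanisms are involved.

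- **Treatment phase: time never recorded.** If the next visit comes more than 7 days after insertion, the sensor cannot cover the whole interval. Weeks 2 to 4 may then rest on fewer than 7 recorded days.
- **Follow-up: recorded time not analysed.** The SAP counts back from the retrieval visit, while the recording starts at insertion. When the gap exceeds 7 days, the two no longer coincide, and a subject with a complete 7-day recording can contribute only part of it, or none.

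The CGM parameters are among the secondary efficacy endpoints and feed the objective describing the time course after Week 4 (SAP 3.2.1). With 16 subjects per arm, each avoidable loss counts. The episode rate is the more exposed endpoint, because a shorter recording lowers a raw count even when the underlying frequency is unchanged.

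**Working it through.** **The plan's own intervals.** Follow-up: (13 − 12) × 7 = 7 days and (26 − 25) × 7 = 7 days. Treatment phase, from Visit 3 on Day 1: 7 − 1 = 6, then 14 − 7 = 7, 21 − 14 = 7 and 28 − 21 = 7 days. On schedule, every interval is within the stated capacity and nothing is lost.

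**Longest in-window intervals, treatment phase.** Latest day of the next visit minus earliest day of the inserting visit:

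| Visits | Text of 9.5 | Table 6 |
|---|---|---|
| 3 to 4 | 9 − 1 = 8 | 8 − 1 = 7 |
| 4 to 5 | 16 − 5 = 11 | 15 − 6 = 9 |
| 5 to 6 | 22 − 12 = 10 | 22 − 13 = 9 |
| 6 to 7 | 29 − 20 = 9 | 29 − 20 = 9 |

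Time beyond capacity is the interval minus 7, so at most 4 of 11 days (36%) between Visits 4 and 5 by the text, or 2 of 9 (22%) by Table 6. Over the four weeks the worst total is 6 days by the text (visits on Days 5, 16, 20 and 29: 4 + 2) and 4 by Table 6 (Days 6, 15, 20 and 29: 2 + 2).

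**Fewest recorded days per SAP week**, assuming a sensor records from insertion for at most 7 days:

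- By the text: 4 of 7 in Week 2 (in on Day 5, records Days 5-11, Days 12-14 lost); 4 of 7 in Week 3 (in on Day 12, records Days 12-18, Days 19-21 lost); 5 of 7 in Week 4 (in on Day 20, records Days 20-26, Days 27-28 lost).
- By Table 6: 5, 5 and 4. The 4 in Week 4 needs Visit 7 on Day 26; sensor expiry alone costs Week 4 at most 2 days under either set of windows.

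**Follow-up.** Let L be the days from insertion to retrieval, with L above 7. Under the same assumption the recording covers days 0 to 7 after insertion, and the SAP window covers days L − 7 to L. The overlap is max(0, 14 − L).

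| Gap L (days) | Recorded | In SAP window | Recorded but not analysed |
|---|---|---|---|
| 7 | 7 | 7 | 0 |
| 8 | 7 | 6 | 1 |
| 9 | 7 | 5 | 2 |
| 10 | 7 | 4 | 3 |
| 12 | 7 | 2 | 5 |
| 14 to 21 | 7 | 0 | 7 |

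If the ±1 week windows are read as independent, L can run from 12 − 13 = −1 week to 14 − 11 = 3 weeks, that is −7 to 21 days. A gap of 14 days then needs only half a week's slip at each visit in opposite directions: 7 + 3.5 + 3.5.

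**Effect on the endpoints.** Proportional time has recorded time in its denominator, so 4 recorded days instead of 7 reduce precision without mechanically lowering the value; with no recorded day in the window it is undefined. At a constant underlying frequency, the episode count scales with recorded days: 4/7 = 57% of the full-week count, an apparent fall of 43%. The SAP does not say whether an empty window gives a zero count or a missing one.

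**The case against.** - **The follow-up gap is specified.** Protocol 7.1 and 9.5.9 both put retrieval a week after insertion. A coherent reading is that the pair moves together by up to a week and stays 7 days apart. The literal independent reading even lets Visit 9 precede Visit 8, which cannot be meant. This stands as far as intent goes: a reader might infer that gaps of 14 to 21 days are what the plan provides for, and the documents do not support that. But the one-week statements carry no tolerance, the windows are printed separately in 9.5 and Table 6, and a slip of one day already drops a recorded day.
- **The device might keep the latest 7 days.** The protocol does not say whether recording stops or older readings are overwritten. If the latest 7 days were kept, they would match the SAP window and the follow-up loss would disappear. The treatment-phase gap, up to 4 of 11 days, would remain. This stands as a condition on the follow-up result.
- **The extremes are unlikely.** The 11-day interval needs Visit 4 at its earliest and Visit 5 at its latest under the wider windows, and the overview describes weekly returns. True; it would be wrong to infer that Weeks 2 to 4 are generally truncated.
- **Little depends on it.** A reader might take CGM to be the only outpatient efficacy data. It is not: SAP 3.2.1 also lists subject-reported hypoglycemic events, and the time-course objective also covers the clamp measures. Secondary endpoints are descriptive under SAP 7.10.5. A reader might also infer bias between arms. The documents do not show it: randomization is stratified by site, and subjects and staff are blinded. These points limit the severity; they do not remove the mismatch.

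**Conclusion.** The concern holds as a moderate, conditional one. The visit windows permit sensor intervals above 7 days: up to 11, 10 and 9 days by the text, or 9 days each by Table 6. In the treatment phase the consequence is unrecorded time. At follow-up, the one-week text and the separate ±1 week windows conflict, and the SAP's backward count leaves max(0, 14 − L) analysed days for any gap above 7.

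The follow-up figures assume that recording stops 7 days after insertion. The 14 to 21 day cases also need the two windows to be read as independent. Nothing is lost when visits are on schedule. The loss chiefly affects the episode rate, which has no time denominator; proportional time mainly loses precision or goes missing. The primary endpoint is untouched.

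**What to change.** 1. **SAP 7.2.10 and 7.2.10.1.** Define Month 3 and Month 6 as the days actually recorded by the sensor inserted at Visit 8 or Visit 10, up to 7 days. Divide episode counts by recorded CGM time, so that an empty window gives a missing rate and not a zero. The definition works whichever 7 days the device keeps. It needs no new data and costs almost nothing.
2. **Protocol 7.1, 9.5 and Table 6.** Reconcile the one-week statement with the ±1 week windows by timing Visits 9 and 11 relative to the Visit 8 and 10 insertions. The cost is slightly less scheduling flexibility.
3. **Protocol 9.5.4, 9.5.5, 9.5.7 and Table 6.** State one window each for Visits 4, 5 and 7, and aim for sensor intervals of about 7 days within those windows. Re-anchoring the SAP cannot recover days that were never recorded, so this step is needed for Weeks 2 to 4.

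A strict maximum of 7 days chained from visit to visit should be avoided. Under the text windows, Visit 4 on Day 5 would force Visit 5 by Day 12, Visit 6 by Day 19 (outside Days 20-22) and Visit 7 by Day 26 (outside Days 27-29), which would also advance the primary-endpoint clamp.

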### **9.5.3. Visit 3 (Day 1) Start of Treatment Phase**

The subject will arrive to the clinic at about 6-9 am for the planned randomization. The subject will fast after midnight until the end of the hypoglycemia procedure the subsequent day.

The following procedures will be completed:

1. Eligibility Review
2. The subject's CGM, electronic diary, and insulin utilization data will be collected/uploaded to the electronic data capture (EDC).
3. Assessment will be made whether the CGM baseline data meet the criteria of minimum 6 days are recorded using the CGM device. The clinic will be notified within 30 minutes from time of subject data upload as follows:
  - a. If the data do not meet the above criteria, the subject is inserted with another CGM for renewed baseline of CGM period. The visit is rescheduled for a week later and the subject is sent home with instructions for another baseline attempt. Should the second baseline period not yield eligible CGM data, the subject will stop further participation in the procedures.
  - b. If the data meets criteria, the visit proceeds.

The following procedures will be carried out once CGM data is confirmed. This includes a confirmation that the subject did not have a hypoglycemic event, < 70 mg/dL during the 8 hours prior to the induction.

4. A new CGM sensor will be inserted.
5. The subject will be asked of any changes in concomitant medications since their last visit and this will be documented in the CRF.
6. The subject will fill out the Gold Score about hypoglycemia awareness.
7. Urine pregnancy test for women of childbearing potential.
8. The subject will be reminded to refrain from using his or her own insulin until the hypoglycemia induction procedure the following day is complete. However, the subject will withhold their long acting insulin.

9. The Insulin Diary will be collected from the previous visit and a new diary given to the subject to collect the following, daily:
  - Total daily dose
  - Total Daily Bolus
  - Basal Rate
10. IV lines are inserted in both upper extremities. One side will be used for both IV insulin infusion and IV glucose infusion. The other side will be used for venous sampling during the clamp procedure.
11. Collection of venous blood for the following tests as outlined in the Schedule of Activities:
  - CBC/CMP
  - Plasma glucagon (PK) prior to Omnipod placement
12. Plasma glucose is measured using a laboratory quality instrument, e.g. the YSI 2300 or 2900 that will be used for the clamping procedure.
13. Insulin infusion should begin after the baseline venous blood samples are obtained. An IV glucose infusion should be started concomitantly.
14. Assessment of vital signs, including measurement of BP, after a 5-minute seated rest
15. The 100 mg/dL baseline prior to hypoglycemia induction will be assessed for adequacy or initiated as described in section 9.4.1.
  - a. When the baseline has been deemed adequate for at least 60 minutes two sets of blood samples for assessment of counter regulatory hormones will be drawn 10 minutes apart and processed.
16. The hypoglycemia induction including PG determination and hypoglycemia symptoms assessments (Appendix 2) will be executed as described in sections 9.4.2 to 9.4.5.
17. When hypoglycemia at 50 mg/dL has been held for 30 minutes, two sets of blood samples for assessment of counter regulatory hormones will be drawn 10 minutes apart and processed.
18. Treatment allocation and dispensing: The subject will be randomized as described in section 8.4, investigational product and Omnipods for the subject will be retrieved from storage.
19. When PG is >70 mg/dL in the normalization phase (section 9.4.6) the subject will be instructed in the filling and deployment of the OmniPod.
20. The study personnel will ensure the Omnipod flow rate is correctly set per protocol.
21. The subject will fill and deploy the first Omnipod under the observation of study personnel, insert and initiate the device as part of the training so that the subject can do this at home 2-3 days later.
22. The subject will be supplied with sufficient investigational product, Omnipods, and other study materials until the next weekly visit. The subject's training will include instructions to prepare a new Omnipod with the study drug for insertion, every 2-3 days.
23. Each time a new OmniPod is started local tolerability will be assessed as follows:

- a. Subjects will complete a Visual Analog (VAS) questionnaire regarding infusion site discomfort ([Appendix 3](#)) at **10±5** minutes, at **30±5** minutes and again at **180±5** minutes following the injection of study drug.
  - b. Subjects will complete an Injection Site Discomfort Description and Duration Questionnaire at **10±5** minutes post-dosing. If discomfort is ongoing at 10 minutes post-dosing, the questionnaire will be completed again before the subject leaves the clinic to document the final duration.
24. When the normalization procedure is complete and the subject is medically stable for discharge, the next CRU visit, to replenish supplies, will be scheduled. The subject will be reminded to keep his or her iPROmylog diary, bring used and unused Omnipods and investigational product vials back at the next visit.

Approved

#### **9.5.4. Visit 4 – Safety check (Day 7±2)**

This visit can occur at any time of day as is least cumbersome for subject and clinic scheduling. The following will occur.

1. AEs since the last visit will be recorded.
2. Concomitant medication review.
3. Subject data including CGM, insulin utilization, electronic diary data will be uploaded to the MedTronic iPRO2 platform.
4. The subject's Omnipod will be removed.
5. The investigator or sub-investigator will use the modified Draize scales ([Appendix 4](#)) to assess erythema and edema formation at the injection site at 10±5 minutes following removal of the Omnipod. Any injection site with a score > 0 for either erythema or edema at 10 minutes post-dosing will be re-evaluated for both at 60±5 minutes post-dosing. If any scores remain > 1 at the 60-minute evaluation, the subject may leave the clinic but will be instructed to contact study staff if the condition fails to resolve.
6. Investigational Product and Omnipod accountability will be performed
7. The subject will load and initiate a new Omnipod with investigational product.
8. The subject will be given investigational product and Omnipods to cover time to next visit and will be instructed to exchange the Omnipod every 2-3 days.
9. Each time a new OmniPod is started local tolerability will be assessed as follows:
  - Subjects will complete a Visual Analog (VAS) questionnaire regarding infusion site discomfort ([Appendix 3](#)) at 10±5 minutes, at 30±5 minutes and again at 180±5 minutes following the injection of study drug.
  - Subjects will complete an Injection Site Discomfort Description and Duration Questionnaire ([Appendix 4](#)) at 10±5 minutes post-dosing. If discomfort is ongoing at 10 minutes post-dosing, the questionnaire will be completed again before the subject leaves the clinic to document the final duration.
10. The next visit will be scheduled
11. The subject will be reminded to keep his or her iPROmylog diary, bring used and unused Omnipods and investigational product vials back at the next visit

